2.2 RANDOMIZATION

Randomization for all centers will be done through the internet:

www.color2.org (click "investigators")

3 SUMMARY PROTOCOL

3.1 INTRODUCTION & BACKGROUND

Laparoscopic resection of colorectal malignancies is still controversial, mainly due to initial reports on port-site metastases that caused major concern. Although retrospective studies with large numbers of patients now suggest that the incidence of port-site metastases is comparable to the incidence of wound metastases in open surgery, the pathogenesis of these recurrences remains unclear. Experimental studies and one randomized clinical trial (Lacy) indicate that laparoscopic surgery might even result in lower recurrence rates. In this trial comparing laparoscopic versus open colectomy for colonic cancer, an improved 3-year survival following laparoscopic resection was found.

Benefits of laparoscopic surgery in general are less postoperative pain, a shorter recovery period and earlier return to work and daily activities. These benefits are likely to apply to laparoscopic colorectal surgery as well.

With ever advancing technique in laparoscopic surgery, the possibilities for longer and more complex operations are expanding. Along with this trend laparoscopic surgeons are performing more demanding surgical procedures, such as Total Mesorectal Excision (TME) for rectal cancer. We believe that the development of laparoscopic TME procedures should be performed within a trial setting, because long-term results are not established. Within a trial, the technique can be standardized and quality control is assured.

3.2 STUDY DESIGN

The COLOR II trial is a randomized, international, multi center study comparing the outcomes of laparoscopic and conventional resection of rectal carcinoma with curative intent. Clinical and operative data will be collected centrally in the coordinating center in Halifax, Nova Scotia, Canada. Quality of life and costs will be assessed on a national basis.

Prior to the start of the COLOR II trial, a feasibility study will be performed. The objective of this feasibility study is to control quality of laparoscopic TME procedures. Per center, five consecutive TME's are performed, and either recorded or observed by an expert in laparoscopic TME. All resected specimens are pathologically analyzed. Furthermore, each participating center should at least send one unedited video of a laparoscopic TME to the monitoring committee for approval.

3.3 ENDPOINTS

Primary endpoint of the phase III trial is locoregional recurrence rate 3 years postoperatively. Secondary endpoints are disease free and overall survival at three, five and seven years, rate of distant metastases, port-site and wound-site recurrences, macroscopic evaluation of the resected specimen, 8-week mortality and morbidity, quality of life and costs.

3.4 STATISTICS & RANDOMIZATION

Using log rank statistics with a power of 80 % and a type I error of 5%, 1275 patients are needed to detect a difference between both treatment arms of 5% in locoregional recurrence rate 3 years postoperatively, assuming a 10% recurrence rate in the open group. Randomization will be 2:1, laparoscopic versus open resection respectively. Analyses will be on "intention to treat" basis. Randomization is stratified for each participating center, planned procedure, radiotherapy and sex.

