19 STATISTICAL CONSIDERATIONS

19.1 SAMPLE SIZE AND STATISTICAL ANALYSIS

Locoregional cancer recurrence rate of operated patients with cancer stages <IV after 3 years is currently about 10 %. The primary objective of the study is to show that laparoscopic surgery does not lead to an increased locoregional recurrence rate. Equivalence of both treatments is considered to be shown if the resulting two-sided 95% confidence limits of the difference in 3-yrs locoregional recurrence rates excludes a difference greater than 5%. At a randomization ratio of 2:1, and assuming a recurrence rate of 10% in each group, 850 laparoscopic patients and 425 open patients are required to have a power of 80% for this study.

All analyses will be carried out on an "intention to treat" basis: patients, whose randomized laparoscopic operation was converted to an open resection, will be analyzed in the laparoscopic group.

Eight weeks operative mortality, pathological resection margins and complication rates will be compared using the Chi-square test. Locoregional recurrence rate, disease free survival and overall survival will be compared between the two procedures using log-rank statistic, adjusted for center. Exploratory analysis of the prognostic effects of various baseline data will be done using multivariate Cox-regression. Analysis of the primary endpoint will be performed 1.5 - 2 years after inclusion of all patients.

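### Sections 3.4 and 19.1 justify the same 1275 patients by incompatible hypotheses, and only the non-inferiority basis in 19.1 follows from its printed inputs

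*Protocol*

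**What the plan says.** Section 3.4 (Statistics & randomization) gives the test and error rates as "Using log rank statistics with a power of 80 % and a type I error of 5" per cent. It then states that "1275 patients are needed to detect a difference between both treatment arms of 5% in locoregional recurrence rate 3 years postoperatively". The open-arm rate is taken as 10%. Allocation is fixed there too: "Randomization will be 2:1, laparoscopic versus open resection respectively". The section does not say whether the 5% is one- or two-sided, or whether the laparoscopic rate is taken as 5% or 15%.

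Section 19.1 (Sample size and statistical analysis) starts from a different aim: "The primary objective of the study is to show that laparoscopic surgery does not lead to an increased locoregional recurrence rate". Its criterion opens with "Equivalence of both treatments is considered to be shown if the resulting two-sided 95% confidence limits of the difference in 3-yrs locoregional recurrence rates". The condition to be met is that those limits rule out a gap of more than 5 points. The sizing follows: "assuming a recurrence rate of 10% in each group, 850 laparoscopic patients and 425 open patients are required to have a power of 80" per cent. Since 850 + 425 = 1275, this is the number in 3.4.

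Later in 19.1, locoregional recurrence is listed with disease-free and overall survival as an outcome to be compared by a center-adjusted log-rank test. The text does not say how that test relates to the confidence-interval criterion.

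**The concern.** In 3.4 the null hypothesis is no difference, and the 80% is the chance of a significant result when the arms truly differ by 5 points. In 19.1 the null is an excess of 5 points or more, and the 80% is the chance of excluding it when the arms are truly equal. These are different trials that share a sample size.

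The primary conclusion depends on which one is meant. A non-significant log-rank test would not show that laparoscopic surgery avoids an increase in recurrence; it could simply reflect imprecision. A reader who takes the hypothesis from the summary would therefore judge the trial by a test that cannot deliver the objective in 19.1. The log-rank sentence in 19.1 carries the same ambiguity into the full statistical section. The word 'equivalence' adds a third possible criterion, stricter than the one the sample size supports.

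**Working it through.** **Inputs.** From 3.4: 10% open, 5-point difference, power 80%, type I error 5%, 2:1, N = 1275. From 19.1: 10% in both arms, 5-point margin, two-sided 95% interval (2.5% per side), 850 and 425, power 80%. The protocol states no dropout allowance, so none is used, and every patient is taken to contribute a 3-year outcome.

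**1. The basis in 19.1, as non-inferiority.**
- SE = √[0.10 × 0.90 × (1/850 + 1/425)] = 0.01782.
- Power = Φ(0.05/0.01782 − 1.960) = Φ(2.805 − 1.960) = Φ(0.845) = 80.1%.
- Open arm for 80% power: (1.960 + 0.842)² × 0.09 × 1.5 / 0.05² = 423.8, so 424. With 848 laparoscopic the total is 1272, against 1275 stated.

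This reproduces from printed inputs alone.

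**2. The basis in 3.4, log-rank at two-sided 5%.** The hazard ratio (HR) under proportional hazards is ln(1 − p_lap)/ln(0.90). Events D = 1275 × (0.10 + 2 p_lap)/3. Schoenfeld power is Φ(√(D × 2/9) × |ln HR| − 1.960).

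| Laparoscopic v open | HR | Events at 1275 | Power at 1275 | N for 80% |
|---|---|---|---|---|
| 5% v 10% | 0.487 | 85 | Φ(3.128 − 1.960) = 87.9% | 1022 |
| 15% v 10% | 1.543 | 170 | Φ(2.664 − 1.960) = 75.9% | 1410 |

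The N column is before rounding events up to whole numbers; with rounding it is 1035 and 1418. Other 2:1 formulas (Freedman, pooled and unpooled proportions, continuity-corrected, arcsine, HR as a ratio of rates) stay within 871 to 1110 for 5% v 10% and 1410 to 1669 for 15% v 10%. None gives 1275.

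**3. The basis in 3.4, log-rank at one-sided 5%, harm only.** Take 15% v 10% and set HR = 15/10 = 1.5:
- Events = (1.645 + 0.842)² / [(2/9) × (ln 1.5)²] = 169.2, so 170.
- Average event probability = (2 × 0.15 + 0.10)/3 = 0.1333.
- N = 170/0.1333 = 1275.

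This is an exact match. With the HR that the same 3-year rates imply (1.543), it is 149 events, N = 1118, and power at 1275 of 84.6%. Other one-sided 2:1 formulas for 15% v 10% run from 1118 to 1326. One-sided tests for benefit (5% v 10%) need 686 to 870 and do not match.

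**4. The word 'equivalence' in 19.1, if both limits had to lie within ±5 points.**
- Power at 1275 = 2 × Φ(0.845) − 1 = 60.2% (simulation: 60.6%).
- Open arm for 80%: (1.960 + 1.282)² × 0.09 × 1.5 / 0.05² = 567.4, about 1702 in total (1704 with whole 2:1 arms).

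**The case against.** The best defense of 3.4 is that it never says two-sided. The objective in 19.1 concerns an increase, so a one-sided test for harm is a natural reading, and step 3 shows that one standard calculation then returns 1275 exactly. This stands. A reader might infer that 3.4 simply fails to reproduce, or that its power differs from 80% in either direction. The document does not support so flat a statement, because two-sidedness is an assumption added to 3.4. Nor does 3.4 speak of superiority; it speaks of detecting a difference.

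The match does not reconcile the sections. It needs two choices that 3.4 does not state (one-sided alpha, harm only) and a ratio of risks used as a hazard ratio. Even granted, a one-sided 5% test conflicts with the 2.5% per side in 19.1, and its null and alternative are still reversed relative to 19.1.

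A second defense is that 3.4 is one sentence in a summary, while 19.1 fixes the objective, margin, rates and criterion. That also has force. It counts against inferring that the trial is free to choose superiority or non-inferiority after the fact. But the log-rank comparison of locoregional recurrence stands in 19.1 itself, so the difference-test framing is not confined to the summary.

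Third, 'equivalence' may be loose wording. The one-directional objective and the arithmetic in step 1 both point that way.

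**Conclusion.** The point holds as an inconsistency in the stated hypothesis and power basis for the primary endpoint. It is not an error in the number 1275, which is right for non-inferiority at a 5-point margin with 10% in both arms (80.1% power).

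The figures of about 88% and 76% for 3.4 hold only at two-sided 5% with proportional hazards. On a one-sided reading for harm 3.4 can give 1275, but at a different alpha and for a different hypothesis from 19.1. On every reading tried, the two sections disagree.

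A reader might infer from the word 'equivalence' that the trial has only 60% power. That figure applies only if both confidence limits must lie within 5 points, and the stated objective in 19.1 runs in one direction. The planned non-inferiority comparison is not underpowered on the protocol's assumptions.

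**What to change.** Three wording changes:

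1. In 3.4, replace the sample size sentence with: *1275 patients (850:425) give 80% power to show non-inferiority, i.e. upper limit of the two-sided 95% CI for laparoscopic minus open below 5 points, assuming 10% in both arms.*
2. In 19.1, replace 'Equivalence' with 'Non-inferiority'. If two-sided equivalence really is intended, restate the power as 60%.
3. In 19.1, state that the primary conclusion rests on the confidence interval for the difference in 3-year locoregional recurrence rates, and that the center-adjusted log-rank test of that endpoint is supportive only. Without this, a difference test would still stand beside the interval criterion after the first two changes.

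The cost is an edit to two sections. Patient numbers and data collection do not change.

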3.5 MAIN SELECTION CRITERIA

Patients with a single rectal cancer at less than 15 cm from the anus at rigid rectoscopy, eligible for surgery with curative intent, can be included. Not included are patients who have local excision of a rectal cancer. Also not eligible are patients with concomitant metastases or other malignancies, with malignancies in their medical history or with signs of acute obstruction.

3.6 FOLLOW-UP

Patients will be examined at least once a year for seven years. Every year, up to 7 years after surgery, anamnesis and physical examination are performed. In case of recurrent disease, follow up should be until 3 years from the time of diagnosis of recurrence.

4 INTRODUCTION

4.1 EPIDEMIOLOGY

Colorectal cancer is the third most frequent malignancy in males, after prostate and lung cancer, and the second most frequent malignancy in females, after breast cancer. Every year, colorectal cancer afflicts 221000 new patients and causes 111000 deaths in the European Union. Death rates of colorectal cancer in Western European countries vary from 17 to 19 per 100,000 population.

In the Netherlands yearly 8.600 patients are newly diagnosed with colorectal cancer and 25 % of these tumors is located in the rectum.

About 75 % of all rectal cancer patients can be treated by surgery with curative intent, of which 10% is cured by local excision. In about 25% of patients, extensive surgery is not an option because of poor performance or advanced stage cancer.

4.2 SURGERY FOR COLORECTAL CANCER

Adequate resection of colorectal cancers is the only curative treatment. The tumor-bearing bowel is excised with its accompanying mesentery containing the vascular supply and the lymph draining vessels. Survival after resection of colorectal malignancies depends on stage of disease, radicality of resection and adjuvant therapy, surgical technique being critical both in respect of cure and local recurrence. Conventional surgery for colorectal cancer requires extensive laparotomy. Preferred margins for resection of the bowel vary, depending on the site of the tumor, from 2 to 5 cm. Sufficient resection of lymphatic tissue adjacent to the tumor is considered essential by most colorectal surgeons.

The limited workspace in the lower pelvis and the bony structures surrounding it, make it difficult to operate on the rectum and impede complete resection of rectal cancer. Until the late seventies blunt dissection of the rectum along the presacral fascia was performed, which was distally directed cone-wise to allow for a low anastomosis. Lateral excision was often incomplete in this procedure with high rates of local recurrences as a consequence, up to 45 %, were reported. A new procedure, Total Mesorectal Excision (TME) was introduced by Heald in 1982.

Sharp dissection along anatomical planes results in a more complete resection, especially on the lateral sides. Local recurrence rates dropped significantly because of this. In addition, the presacral nerves and vessels are better preserved, resulting in better outcome considering bladder and sexual function postoperatively.

The low recurrence rates reported by surgeons who specialize in TME are now reproduced by Kapiteijn et al. in a multi-center randomized controlled trial [1]. In this trial the TME technique was standardized and extensive training in the technique was offered, allowing for very reliable results.

Currently open TME must thus be regarded the pillar of cure for rectal cancer and the gold standard against which any modification of the technique must be judged.

4.3 LAPAROSCOPIC SURGERY FOR COLORECTAL CANCER

Recently, Lacy et al published the first long-term results of a randomized trial comparing laparoscopic colectomy versus open colectomy for the treatment of colonic cancer. This study demonstrated improved 3-year cancer related survival following laparoscopic surgery compared to open surgery (91% vs 74% respectively). The observed benefit could mainly be attributed to lower tumor recurrence and a longer overall survival of patients with stage III colonic cancer [2]. The authors concluded that laparoscopic colectomy is preferred to open colectomy in patients with colonic cancer. Results of this study have to be interpreted with great care because it represents a single institution experience with a relative small number of patients. Results of large multi-center trials will have to be awaited. Interim analysis of these randomized trials have not shown significant differences of recurrence rate so far, as none of the trials have ceased including new patients for this reason.

Laparoscopic colorectal surgery was first reported in 1991 by Jacobs et al [3]. In spite of the technical complexity and initial high financial costs of laparoscopic colorectal surgery, feasibility to use laparoscopic techniques for almost the entire spectrum of colorectal surgery has been established [4-10]. In a registry, supported by the American Society of Colon & Rectal Surgeons and the American College of Surgeons, of 453 laparoscopic resections for colorectal cancer, subjective violation of cancer principles occurred in only 1 percent of patients [11].

However, first reports on abdominal wall metastases after laparoscopic resection of colorectal cancers have caused major concern [12]. Comparison of the incidences of abdominal wall metastases after open and laparoscopic colectomy is not possible because true incidence rates are unknown. Incidences of abdominal wall metastases vary from 0.69 % to 16.6 % [13-16] following open resection for colorectal cancer and from 0.6 % to 21 % [11, 12, 17, 18] following laparoscopic resection of colorectal cancer. Review of laparoscopic resections for colorectal cancer has shown the majority of reported abdominal wall metastases to occur in patients with loco-regionally advanced disease or diffuse peritoneal carcinomatosis [8, 19]. Recent reports on laparoscopic colon resection for malignancies do not show an increased incidence of abdominal wall

metastases [20, 21]. In a recent review of current literature the incidence of port site metastasis is 1% or less[22]. Experience of the surgeon and standardization of the technique seem to play an important role [23-25].

The pathogenesis of abdominal wall metastases remains unresolved. Inadvertent grasping of the tumor and extraction of the tumor through narrow incisions of the abdominal wall are likely to play an important role. Precise localization of the tumor and protection of either the abdominal wall or the specimen during extraction are therefore used by most experienced surgeons. Whether the increased intra abdominal pressure or the use of CO₂ gas to establish the pneumoperitoneum compromise cancer free survival remains uncertain. Some experimental studies have shown that gasless laparoscopy results in less tumor growth [26].

Laparoscopic surgery appears to be associated with less operative trauma and blood loss than open surgery. These factors are considered beneficial for survival [27, 28]. Experimental studies have shown that tumor take and growth are significantly less after laparoscopic surgery [29, 30]. Clinical studies on interleukin-6 response to open and laparoscopic colectomy showed significant lower levels of interleukin-6 after laparoscopic procedures, indicating a lower degree of surgical trauma and less attenuation of immunity [22, 31].

The motives to approach colorectal disease laparoscopically are similar to those of laparoscopic cholecystectomy. Compared to open cholecystectomy, laparoscopic cholecystectomy is associated postoperatively with less pain, reduced respiratory impairment, earlier return of gastro-intestinal function, earlier mobilization, shorter hospital stay, earlier return to daily activities and work, improved cosmetic results and less incisional hernias [32, 33]. These same advantages are likely to apply to laparoscopic colorectal surgery.

4.4 LAPAROSCOPIC SURGERY FOR RECTAL CANCER

With ever improving technical assets associated with laparoscopic surgery, the possibilities for longer and more complex operations are expanding. Along with this trend, laparoscopic surgeons are exploring new endoscopic surgical procedures. TME for rectal cancer is one of the more recent procedures to be performed laparoscopically. The limited workspace in the lower pelvis lends itself well for a laparoscopic approach and technical advances make laparoscopic resection possible. Reports on laparoscopic TME are still rare because the technique is developed only recently and performed by a select number of surgeons. Few highly skilled laparoscopic surgeons have engaged laparoscopic TME so far [34-36].

The outcome after resection of rectal cancer is mainly dependent on the extent of resection according to TME principles. Few case reports and short non-randomized series are published so far. In these series extent of resection upon pathological examination of the resected specimen was comparable to open resection [35, 37]. To our knowledge, only one randomized controlled trial, the CLASICC trial, has also addressed open versus laparoscopic resection for rectal cancer. However, results of the CLASICC trial have not been published.

We believe the laparoscopic approach to rectal cancer should not be performed outside a trial setting, because long term results on local recurrence are unknown. Within a trial setting, the technique can be standardized and quality control is performed. Postponing such a trial could result in incorporating laparoscopic TME into clinical practice before its exact role is established in comparison to conventional techniques. A similar process has occurred in the introduction of laparoscopic cholecystectomy [38], where randomized controlled trials became available after incorporation of the technique into general practice.

Laparoscopic surgery for colon cancer was performed around the world, including Western Europe without any proof of this minimally invasive technique being associated with equal or better survival than conventional surgery. Such practice was not desirable and the COLOR trial, a randomized clinical trial comparing both techniques, was instigated. For resection of the colon, operating on patients with benign disease could first optimize the technique. However, TME can only be developed by operating on patients with malignancies of the rectum, because performing a TME for benign disease is rare.

Therefore we consider it important to start a trial at this moment, as standardization of the technique in an early phase is required. Introduction of laparoscopic TME in surgical practice, without prove that it will provide at least similar results as open TME, is undesirable.

4.5 ADJUVANT THERAPY

Extensive studies have been performed throughout the years to investigate the efficiency of many different regimes in controlling local recurrence. With the rise of the TME procedure, with its low recurrence rate, it is now reinvestigated what adjuvant therapy is best in optimizing local recurrence rates and long-term survival. Survival benefits for most regimes have to be proven again and benefits of adjuvant therapy have to be weighed against additive morbidity. In a recent publication, Kapiteijn et al showed that significantly less local recurrences occur after short preoperative radiation with 5*5 Gy in patients with rectal cancer (overall recurrence rate 8.2 vs. 2.4 respectively)[1]. Although no survival benefit was found, this might be caused by the relatively short follow-up of 2 years. The operative procedure was extensively standardized and

Post-operative chemotherapy is not standard treatment in rectal cancer. Chemotherapy is predominantly applied in randomized clinical trials.

